6.0 Research Data Protection and Reporting

6.1 Data Management and Confidentiality

A. Data Analysis Plan

Participants will be randomized into the 3 arms using block randomization. Analyses will be conducted with SAS 9.4 and R 3.2 or updated versions. Outcome variables, along with baseline and follow-up (as applicable) demographic, clinical and psychosocial factors described above, will be summarized by study arm using standard descriptive statistics such as means (standard deviations) for continuous variables and tabulations for categorical variables. Although we do not anticipate baseline differences in the distribution of measured factors between the randomly assigned arms, we will assess for statistical differences using appropriate parametric and non-parametric tests. While the specific aims along with the analyses are described below, some of the analytical strategies across the aims are described as follows: 1) The key study outcomes will be reported that account for missing data using multiple imputation and intent-to-treat (ITT) approaches. Multiple imputation under the Missing at Random assumption will be applied using a Markov Chain Monte Carlo method¹⁸⁶ via PROC MI in SAS, given the expected pattern of non-monotonic missing data. A post hoc approach will address the influence of missing not at random (MNAR) and the effect of attrition on outcomes of interest. Sensitivity analyses will be performed to assess alternative multiple imputation techniques upon the extent of MNAR influences. 2) Multiplicity will be adjusted for the primary outcome analysis using the Holm's adjustment procedure, which guarantees strong error control.¹⁸⁷ The SAS MULTTEST procedure will be used with the marginal p-values. For secondary endpoints, no multiplicity adjustment is considered. All tests will be two-sided. The effect sizes and 95% confidence intervals (CIs) of all outcomes using both ITT, per protocol, and multiple imputed data will be reported regardless of statistical significances.

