who desire but did not access CGRA. Evaluation of the incremental effect will be assessed by comparing the difference of the primary outcome between changed intervention arms (UC to TP/TCN; TP to TCN). For those that availed themselves of “free” CGRA provided through the study, we will describe patient preferences by study arm and other factors (e.g., age, ethnicity, residence area, education, income, literacy, psychosocial factors, and language preference). Model selection with multiple variables will be conducted using AIC and BIC approximation criteria, while including theoretically and practically relevant variables. **Aim 2** tests whether there are differences across the 3 study arms with regard to uptake of genetic testing for HBOC at 6 and 12 months. Similar to Aim 1, multivariable regression modeling approach will be performed for the binary outcome (genetic testing yes vs. no) with the main covariate of arm and other confounding variables at each time point. Then, generalized linear mixed effects model (GLMM) will be employed for the two time point outcomes, using binomial distribution with logit link function and adjusting for the correlation within the same subjects to estimate the behavior trend over time. **Aim 3** compares cognitive and affective intermediate endpoints among women in the 3 study arms and explores potential underlying theoretical mediating and moderating mechanisms that will further specify and elucidate significant 6-month and 12-month intervention effects, if such effects are observed. The study arms will be compared with regard to beliefs (threat and efficacy), informed decision making indicators (knowledge, decisional conflict, and decision regret) and emotional factors (cancer worry and fear). Arm comparisons will be based on differences in least-square mean changes from baseline to 6 months (including values from the 1-month survey) from an analysis of covariance model containing terms for study arm with baseline scores for as a covariate. Structural equation modeling (SEM) for the hypothesized meditational pathways will be conducted with the procedure of CALIS in SAS and the ‘sem’ package in R. Before the SEM, all variables in the modeling will be centered with means zero. The SEM will focus on (1) specifying structural equation models; (2) interpreting the model fit statistics and estimation results; (3) testing model with the arms; and (4) analyzing direct and indirect effects. Mediators of intervention effects include threat appraisals, response efficacy, self-efficacy, knowledge, recommendation about CGRA measured at one-month post intervention. Several indices will be used to assess the adequacy of overall model fit: Comparative Fit Index, Standardized Root Mean-Square Residual, and Root-mean Square Error-of Approximation.¹⁸⁸ The interventions may not be beneficial for all study participants. Thus, sensitivity/moderation analysis will be done to identify subgroups for which the intervention has or does not have an effect (e.g., age, diagnosis, time since diagnosis, rural/urban, education level, literacy, acculturation, language preference, close at-risk relative, household income, familism, family support of CGRA, provider recommendation, and cost, travel and time barriers). This will provide important information about subgroups who are particularly receptive or resistant to the effect of each intervention.

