Genetic Risk Assessment for Cancer Education and Empowerment Project (GRACE)

NCT03326713

January 16th, 2025

GRACE Statistical Analysis Plan

Biostatisticians blinded to study arm assignment performed an intent-to-treat analysis using SAS v9.4, and RMediation package available in R. Summary statistics of baseline patient sociodemographic variables were compared among treatment arms using ANOVA and χ^2 tests. Pearson correlation coefficients were calculated to discern potential correlations between the selected theorized mediator variables. We calculated Cronbach's alpha to ensure internal consistency (the extent to which their respective items measured the same construct) across measures at baseline and the one-month follow-up.

Logistic regression was used to compare the percentage of CGRA intentions reported at the one-month follow-up between study arms; odds ratios and 95% confidence intervals (CIs) were calculated. We leveraged mixed model analysis to assess longitudinal between-treatment-arm and pre-to-post-differences in the scores for CGRA intentions and each theorized mediator variable. (The approach also accounted for repeated measures in our study design, as well as the 95% CIs, using linear contrasts.) We then performed mediation analysis to assess whether improvement in CGRA intentions was mediated by pre-to-post changes of the theorized mediator variables.

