Multiple imputation assumed missing at random and was based on verified CGRA within 6months and demographic information; having a primary care provider; cancer site (breast v ovarian cancer); and number of first- and second-degree relatives with cancer, as well as the a priori interaction of the intervention with potential effect modifiers: race, ethnicity, health insurance status, literacy level, and household income. Ten imputed data sets were generated using IVEware with sequential regression, and Rubin's rule was applied to combine results using SAS Proc Mianalyze. Odds ratios, CGRA percentages, and 95% CIs were conducted using SAS v9.4.

With a final sample size of at least 212 per arm and 3% of CGRA for TP or UC, the minimum detectable OR for comparisons between TCN and TP or between TCN and UC is 1.86 with 80% power and 5% overall type I error rate (2.5% for each comparison) after multiplicity adjustment.

Demographic and clinical characteristics of participants were compared among three arms using ANOVA and chi-square analysis. The mediators at baseline and 1 month were compared (within arms and between arms) using paired *t*-tests and two-sample *t*-tests; CGRA uptake at 6 months was compared using a chi-square test.

Generalized structural equation modeling (GSEM) was used for mediation analysis because CGRA uptake is a binary outcome. All 1-month cognitive and emotional mediators were controlled for baseline levels and all scores were standardized. Maximum likelihood estimation was used for estimating regression coefficients/parameters. Indirect effects were estimated, and a bootstrapping method (1,000 replications) was used to construct 95% confidence intervals.

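### SAP item 3 compares the 1-month mediators between arms with t-tests that name no baseline covariate; ANCOVA on the baseline score, as in protocol Aim 3, would be more efficient at almost no cost

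*SAP*

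**What the plan says.** **SAP item 3** (mediators of the intervention effect): "The mediators at baseline and 1 month were compared (within arms and between arms) using paired" t-tests and two-sample t-tests. It names no covariate for these tests and does not say whether the two-sample tests are on 1-month scores or on changes. For the generalized structural equation model (GSEM) that follows, it adds: "All 1-month cognitive and emotional mediators were controlled for baseline levels and all scores were standardized".

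**Protocol section 6.1.A, Aim 3**: arm comparisons rest on "differences in least-square mean changes from baseline to 6 months (including values from the 1-month survey) from an analysis of covariance model", the model "containing terms for study arm with baseline scores for as a covariate".

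**SAP item 1**: "Logistic regression was used to compare the percentage of CGRA intentions reported at the one-month follow-up between study arms". Covariates are neither listed nor excluded. The next sentence reads: "We leveraged mixed model analysis to assess longitudinal between-treatment-arm and pre-to-post-differences in the scores for CGRA intentions and each theorized mediator variable".

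**Protocol Table 5 (section 1.8)** shows baseline and 1-month collection for perceived risk, threat and efficacy, knowledge, fear, worry, distress, provider recommendation and CGRA intention. Decisional conflict about CGRA and social support have a 1-month value but no baseline.

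**The concern.** In a randomised comparison of a score that was also measured at baseline, a test on the follow-up score alone leaves chance baseline imbalance in the arm difference and ignores variance that the baseline explains. The protocol planned to use that information, and item 3 gives no reason for departing from it. The price is power: a real effect on a mediator is more likely to be missed, and these comparisons help a reader judge which mechanisms the interventions moved.

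A second, smaller point concerns the paired tests. Pre-to-post change within one arm mixes the intervention with anything else that changes over a month, including the effect of being surveyed. It is not a randomised contrast. Without a label, a significant change in one arm and a non-significant change in another invites a conclusion that only a between-arm test can support.

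**Working it through.** Neither document states a standard error, power or detectable difference for the between-arm tests on the mediators, so there is no figure of the plan to reproduce.

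**Inputs**
- n per arm: 212, the final size given in SAP item 2. The number of 1-month completers is not given.
- Two-sided tests (protocol 6.1.A: "All tests will be two-sided"). The protocol adjusts no secondary endpoint for multiplicity, so 5% per test is assumed.
- Effect: d = 0.25 SD, an assumption. Protocol 6.1.B speaks only of small to medium effects.
- r, the baseline to 1-month correlation: in neither document. Assumed, and shown from 0.2 to 0.8.

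**Formulas** (equal variances σ², equal allocation)
- t-test on 1-month scores: SE = σ√(2/n)
- ANCOVA on baseline: SE = σ√(2/n) × √(1−r²)
- t-test on change scores: SE = σ√(2/n) × √(2(1−r))
- ANCOVA relative to change score: √[(1−r²)/(2(1−r))] = √((1+r)/2)
- Power ≈ Φ(d/SE − 1.96); difference detectable with 80% power = (1.96 + 0.84) × SE

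**t-test on 1-month scores, n = 212**: SE = √(2/212) = 0.097 SD. Power = Φ(0.25/0.0971 − 1.96) = Φ(0.61) = 73%. Detectable difference = 0.27 SD.

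**ANCOVA, n = 212**

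| r | SE ratio to 1-month t-test | SE reduction | Power at d = 0.25 | Detectable d | SE ratio to change score |
|---|---|---|---|---|---|
| 0.2 | 0.980 | 2.0% | 75% | 0.27 | 0.775 |
| 0.3 | 0.954 | 4.6% | 77% | 0.26 | 0.806 |
| 0.4 | 0.917 | 8.3% | 80% | 0.25 | 0.837 |
| 0.5 | 0.866 | 13.4% | 84% | 0.24 | 0.866 |
| 0.6 | 0.800 | 20.0% | 90% | 0.22 | 0.894 |
| 0.7 | 0.714 | 28.6% | 95% | 0.19 | 0.922 |
| 0.8 | 0.600 | 40.0% | 99% | 0.16 | 0.949 |

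With 170 per arm (about 80% of 212, the protocol's retention assumption), power is 64% for the t-test and 76%, 82% and 90% for ANCOVA at r = 0.5, 0.6 and 0.7. At the protocol's 182 per arm, the detectable difference falls from 0.294 SD to 0.254 (r = 0.5) or 0.210 (r = 0.7).

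These are reductions in standard error. The variance reduction is r²: 25% at r = 0.5 and 49% at r = 0.7.

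**Logistic comparison of 1-month intention (item 1).** The formula does not carry over to an odds ratio. In a simulation (600 runs, 182 per arm, latent shift 0.3 SD, adjustment for the continuous baseline score), the SE of the log odds ratio rose with adjustment, from 0.213 to 0.235 at latent r = 0.5 and from 0.214 to 0.264 at r = 0.7. Power still rose, from 65% to 73% and from 63% to 77%, because the conditional log odds ratio is larger.

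**The case against.** The strongest reply is that the SAP already uses baseline where it counts. In the GSEM, the 1-month mediators are controlled for baseline, so the arm-to-mediator path is close to the ANCOVA asked for. The item 1 mixed model covers intention and each theorized mediator across arms and time. The t-tests sit next to the demographic comparisons and may be meant as description. A two-sample t-test between randomised arms is unbiased and keeps its error rate.

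Much of this stands. A reader might infer that the SAP throws the baseline values away; it does not. What remains is narrower. The baseline control is stated for the mediation model, and the SAP does not say that the path estimates replace the t-tests as the reported arm comparison. The mixed model belongs to another analysis. If it leaves baseline means free by arm, its arm-by-time contrast is a change score, which at r = 0.5 has the same standard error as the 1-month t-test (√(2 × 0.5) = 1).

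Three further inferences are tempting and unsupported:
- **That the protocol prescribed a 1-month ANCOVA.** Its model concerns change to 6 months, including the 1-month values. Applying the same adjustment at 1 month is a reasonable extension, not a quoted requirement. Intention is not among the variables it lists for that comparison.
- **That the intention model is unadjusted.** Item 1 is silent on covariates.
- **That item 3 treats a paired test as a treatment comparison.** It separates within-arm from between-arm tests. The request is only for a label.

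**Conclusion.** The point holds as one of efficiency and clarity, not validity. As written, the item 3 between-arm tests name no baseline covariate, differ without explanation from the protocol's baseline-adjusted approach, and sit beside model-based analyses without a statement of which carries the inference.

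The size depends on an r that the documents do not give, and on whether the t-tests use 1-month scores or changes. A reader might take the figures at r = 0.5 to 0.7 as an established loss of 13% to 29%. They are illustrations within the 2% to 40% range, they describe standard errors of mean differences, and they do not apply to the odds ratio for intention. The power figures rest further on the assumed d = 0.25 and on 212 women per arm with 1-month data. The comparisons are secondary, so the primary analysis of verified uptake is untouched.

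**What to change.** **SAP item 3.** Make ANCOVA of the 1-month score on arm and baseline score the inferential between-arm comparison for TCN vs UC, TCN vs TP and TP vs UC, wherever Table 5 provides a baseline. Keep an unadjusted comparison for measures without one. Label the paired within-arm tests descriptive. If the t-tests are retained as description, say whether they are on scores or changes. Report the observed r, so that the actual gain can be seen.

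**SAP item 1 (optional).** State whether the 1-month logistic model is adjusted, and consider adding baseline intention. This changes the target: the odds ratio becomes conditional on baseline intention and is not directly comparable with the unadjusted one. The benefit is power, not a smaller standard error. State which odds ratio is reported.

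**Cost.** A few lines of SAP text and, since item 3 describes a completed analysis, a rerun on data already collected. Women without a baseline score on a given measure need a stated rule; the multiple imputation already planned could cover them.

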AIM 4: Perform an economic evaluation alongside this randomized controlled trial to estimate the cost effectiveness of the two interventions compared to each other and usual care, for uptake of CGRA services from the societal and payer perspectives. This aim provides information about the value of the interventions from both societal and payer perspectives, given a cost per effect measure and the uncertainty surrounding the estimate.

[figure not shown]
B. Hypotheses / Research Question(s)

Primary Hypothesis: Compared to UC, CGRA (genetic counseling) uptake at 6 months (primary outcome) will be highest among women participating in the TCN arm followed by women participating in the TP arm.

1.2 Research Significance (Briefly describe the following in 500 words or less):

HBOC Cancer Risks and Genetic Risk Prediction. Identification of individuals at increased risk of HBOC is crucial for cancer survivors and their families to benefit from biomedical advances. In 2015, approximately 254,000 new cases of ovarian cancer and female breast cancer were diagnosed in the U.S. Germline mutations in the BRCA1 and BRCA2 genes account for 5-10% of breast cancers and 15% of ovarian cancers.¹⁻³ This translates to 14,000-27,000 high-risk cancer survivors who may be impacted by HBOC. Women with inherited HBOC gene mutations who have had breast cancer are at higher risk of ovarian cancer and a second breast cancer (Figure 1), and possibly other cancers.⁴

Technological advances in DNA sequencing have now made it possible to test multiple genes simultaneously using multiplex gene panels.^{2,5-18}

[figure not shown]

CGRA Personalizes Care and is Recommended for

High-Risk Breast and Ovarian Cancer Survivors. CGRA is an evidence-based strategy that informs medical management options that can improve outcomes.^{14,17,19} CGRA involves genetic counseling +/- genetic testing. There is evidence that CGRA by genetic professionals improves accuracy of risk perceptions, enables informed decision making, personalizes care, and does not cause adverse psychological outcomes.^{14,16,20-22} National

organizations have issued guidelines recommending CGRA for breast and ovarian cancer survivors who may be at risk for HBOC.^{17,20,23,24} CGRA in HBOC survivors impacts public health (Figure 2).^{4,17} If a mutation is identified, testing for the known gene mutation can be offered to relatives to determine if they have the cancer predisposition.^{20,25}

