All recruitment materials, surveys, and intervention materials will be available to participants in English or Spanish, depending on their preference. The TCN session will be conducted in English or Spanish, depending on the participant's preference. Spanish materials will be submitted to the IRB after the English materials have been approved. To further facilitate communication, Spanish speaking participants and study staff may use over the phone translation services.

There will be 4 surveys over the course of the study period (baseline, 1 m, 6m, 12 m) and will include different components as described below. These are developed at the prime site.

CGRA Decision and Genetic Test Uptake: Participants who have CGRA within 6 months of the intervention (or baseline survey for UC arm) will be considered “completers” of CGRA for the primary outcome. The primary outcome is medical record verified CGRA delivered by the 6-month follow-up. Those reporting that they had CGRA will be asked to sign a medical release form so that we may verify their self-reported CGRA. This approach is extremely feasible and has been successful in ours^{41,134} and others^{135,136} prior work. We will track the type of provider (e.g., physician, genetic counselor, etc.) who provided CGRA and document their genetics training via the documentation form. Using the same strategy, we will assess CGRA utilization at 12 months. Through the medical record release signed by patients, self-reported genetic testing (including type of test and test result) will also be medical record verified at 6 and 12 months.

Sociocultural Factors and Cues to Action: 1) Sociodemographics: age, gender, education, household income, financial status, marital status, rural-urban community area code,¹³⁷ living biological children, and health insurance status, country of origin, years lived in the U.S; 2) Medical history: personal/family history of cancer, cancer stage, health status, co-morbidity index; 3) Acculturation: Short Acculturation Scale;¹³⁸ 4) Family and friends social support and encouragement to obtain CGRA;^{41,139,140} 5) Family orientation: The Familism Scale;¹⁴¹ 6) Brief Fatalism Scale;^{142,143} 7) Health System Distrust;¹⁴⁴ 8) Receipt of a physician/provider recommendation for CGRA; and 9) Primary health care provider received tailored letter in the TPN arm.

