Physician/Health Care Provider Recommendation and Communication	x	x	x	x	Will assess whether healthcare providers have discussed participant's risk of HBOC and CGRA, and how participants feel discussing CGRA and genetic testing with health care provider.
Cancer Genetic Risk Assessment (Genetic Counseling)		x	x	x	Participants will be asked whether they have had CGRA, the provider who conducted the CGRA, and the provider's genetics training. CGRA will be medical record verified.
Cancer Genetic Risk Assessment Intention	x	x	x	x	One item will measure future intention to get cancer genetic risk assessment. In follow up surveys, this will only be asked if participant does not report uptake of CGRA
HBOC Genetic Testing Uptake		x	x	x	Participants will be asked whether they have had HBOC genetic testing, what type of genetic test they had, and the facility where the testing was done. Genetic testing will be medical record verified.
HBOC Genetic Testing Intention	x	x	x	x	One item will measure future intention to get genetic testing for HBOC. In follow up surveys, this will only be asked if participant does not report uptake of genetic testing.
Decisional conflict for CGRA: SURE Scale ^{153,154} ($\alpha = 0.86$)		x	x	x	Decisional conflict associated with the CGRA decision will be measured separately with 4 items using the SURE Scale ^{153,154}
Decisional conflict for HBOC genetic testing: Low Literacy Decisional Conflict Scale (DCS)SURE Scale ^{153,154} ($\alpha = 0.86$)			x	x	Decisional conflict associated with the HBOC gene test decision will be measured separately with 4 items using the SURE SCALE ^{153,154}
Decisional satisfaction with CGRA: Satisfaction with Decision Instrument ^{155,156} ($\alpha = 0.90$).			x	x	Decisional satisfaction will be assessed using the Satisfaction with Decision Instrument. ^{155,156} Four questions assess their personal satisfaction with their decision and three additional items assess

					how they feel about their CGRA decision in relation to their family.
Decision Regret Scale ¹⁵⁸ ($\alpha = 0.81-0.92$)			x	x	Five items will ask about regret regarding the decision to have or not have CGRA. ¹⁵⁸
CGRa and HBOC Genetic Testing Facilitators ^{42,126}	x	x	x	x	Facilitators include but are not limited to: help from family, desire to reduce risk of second cancers, and help/referrals from medical professionals.

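### SAP item 3 relates 1-month mediators to CGRA uptake counted from about 30 days before they are measured, so an effect of counselling on beliefs can be read as mediation

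*SAP*

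**What the plan says.** **Mediators.** The Aim 3 text in protocol section 6.1.A plans mediators taken at one month: "Mediators of intervention effects include threat appraisals, response efficacy, self-efficacy, knowledge, recommendation about CGRA measured at one-month post intervention". SAP item 3 follows this: "All 1-month cognitive and emotional mediators were controlled for baseline levels and all scores were standardized".

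**Outcome.** SAP item 3 uses binary CGRA uptake at 6 months. Protocol section 1.8.B states "The primary outcome is medical record verified CGRA delivered by the 6-month follow-up" and sets the start of the window when it says who counts as a completer: "Participants who have CGRA within 6 months of the intervention (or baseline survey for UC arm) will be considered" completers.

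**Survey timing.** Protocol Table 4 places the 1-month survey 30 days after randomisation in usual care (UC) and 30 days after the intervention in targeted print (TP) and telephone counselling and navigation (TCN).

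**Early CGRA.** Table 5 marks the CGRA item at 1, 6 and 12 months: "Participants will be asked whether they have had CGRA, the provider who conducted the CGRA, and the provider's genetics training". The CGRA intention item is skipped at follow-up for women who already report CGRA.

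**Handling.** SAP item 3 adjusts for baseline mediator scores and ten background covariates. Its sensitivity analysis concerns missing data. It mentions no landmark, no term for CGRA before the 1-month survey and no check on timing.

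**The concern.** A mediator has to come before the outcome it is said to produce. Here the first 30 days of the outcome window lie before the mediator is measured. For women counselled in that time, the session may have changed the beliefs recorded at 1 month, and the model credits that change to the path from beliefs to uptake.

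The protocol itself makes this reverse path plausible. Section 1.2 states that "CGRA by genetic professionals improves accuracy of risk perceptions", and perceived threat and knowledge are among the planned mediators. Baseline adjustment cannot help, because early CGRA happens after baseline.

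Aim 3 is meant to explain how the intervention works. A construct wrongly named as a mediator, or a real one hidden, would misdirect any redesign. The randomised comparison of uptake is not affected.

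**Working it through.** **The plan's own figure.** SAP item 3 states at least 80% power for a single-mediator indirect effect of 0.37. It cannot be reproduced, because the path coefficients, event rates and scale behind it are not given. It is not used below.

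**1. Overlap.** TP and TCN: the window opens at the intervention and the survey falls 30 days later. UC: randomisation takes place at the end of the baseline interview and the survey falls 30 days later. In every arm the overlap is 30 / 180 = 17% of the window. If uptake were spread evenly, 17% of events would be early. This is a reference value and not an estimate.

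**2. How many women this means.** Early events per arm = n × uptake × early share, with n = 212 (SAP item 2).
- Protocol planning rates (section 6.1.B), UC 7% and TCN 34%: UC 212 × 0.07 × 30/180 = 2.5; TCN 212 × 0.34 × 30/180 = 12.0.
- SAP item 2 rate for UC, 3%, with an assumed 20% in TCN: UC 1.1; TCN 7.1.

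About 8 to 15 women would carry the problem, mostly in TCN.

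**3. Simulation with no true mediation.**
- Mediator M = 0.4·T + error (SD 1) + d·E, where T is arm (TCN = 1) and E marks CGRA before the survey.
- Uptake depends on arm only. A share f of events is early.
- Path a is the arm difference in standardised M. Path b is the logistic coefficient of M given arm. A false positive is a 95% interval for a × b, simulated from the two estimates, that excludes 0.
- 212 per arm, 3,000 replicates. The values 0.4, d and f are assumptions; the documents give none of them.
- Simplifications: one mediator, two arms, no covariates. The SD is that of the mediator after baseline adjustment.

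False-positive rate for d = 0.5 to 1.0 SD:

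| Early share f | UC 7%, TCN 34% | UC 3%, TCN 20% |
|---|---|---|
| 0% | 5% | 5% |
| 10% | 7–12% | 7–9% |
| 17% | 9–26% | 8–19% |
| 25% | 17–47% | 13–34% |
| 50% | 48–96% | 34–83% |

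Leaving out women with early CGRA returns the rate to 4–6% in every row.

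**4. Direction.** With d = −0.5 SD (CGRA lowers the score) and rates of 7% and 34%, the spurious indirect effect is negative: about −0.02 at 10% early, −0.03 at 17% and −0.08 at 50%. With d = +0.5 SD it is about +0.02, +0.03 and +0.11.

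**5. Arm-to-mediator path.** Shift in a = d × f × (TCN rate − UC rate). At d = 0.5 and f = 25%: 0.5 × 0.25 × 0.27 = 0.03 SD, against an assumed 0.4 SD. This part is minor.

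**6. Cost of the landmark when mediation is real.** With a true log odds ratio of 0.5 per SD and no reverse effect (rates 7% and 34%), power falls from about 95% to 90% at 25% early and to about 76% at 50% early. The indirect effect shrinks from 0.20 to 0.19 and 0.17.

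**The case against.** The best reply is that the overlap is real but short, and that neither its direction nor its size is documented. Most of this stands.

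- **Direction.** A reader might infer that the model must overstate mediation. Section 1.2 supports only greater accuracy of risk perceptions, which can mean correcting an overestimate downwards. The same sentence says CGRA does not cause adverse psychological outcomes, and it does not mention self-efficacy or response efficacy. Step 4 shows that the sign can reverse.
- **Size.** A reader might take the 50% row as the likely harm. Nothing supports it: it is three times the even-spread share. TCN is delivered in stages (action plan, provider letter, follow-up calls), and its readiness question looks ahead six months. The delay of up to 30 days between baseline and intervention does not widen the overlap, because the TP and TCN window starts at the intervention.
- **Anticipation.** Asking about CGRA at 1 month is routine. It shows that early uptake was possible and can be identified, not that it was common.
- **Silence.** SAP item 3 is a methods extract tied to a published article. It does not say that early events were kept. Their inclusion follows from the outcome definition in the protocol, and any timing check reported elsewhere cannot be seen here.
- **Remedy.** A reader might want the landmark as the main analysis. It selects women on an event after randomisation that depends on arm and, if mediation is real, on the mediator, and it loses power (step 6). That argues for a sensitivity analysis.

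What the reply does not answer is the time order itself. Nothing in item 3 removes or models it, and a count of early events would show whether it matters.

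**Conclusion.** The point holds as a matter of time order: the outcome window opens about 30 days before the mediators are measured, and item 3 as written neither counts nor separates CGRA in that interval. An effect of counselling on beliefs can therefore be read as mediation, or can mask it.

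The size is unknown because the early share is not given. With 10% early or less, the false-positive rate stays near nominal unless CGRA shifts the mediator strongly (12% at worst here, at 1.0 SD). With 17% early it is roughly 8% to 26%. Both rest on an assumed CGRA effect of 0.5 to 1.0 SD, an assumed arm effect of 0.4 SD on the mediator, and the uptake rates listed above.

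A reader might go on to infer that mediation results from this model are artefacts. The documents do not support that. This is a cheap improvement to an exploratory aim.

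**What to change.** In SAP item 3:

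1. Report, by arm, the number of verified CGRA events dated before each woman's 1-month survey.
2. Add a landmark sensitivity analysis: repeat the GSEM among women without CGRA by their 1-month survey, counting CGRA only from that survey to 6 months.
3. Keep the all-uptake model as the main analysis, and claim mediation by a construct only if the two agree. Judge agreement on the sign and size of the indirect effect with its interval, since the landmark has less power and significance alone would be too strict.

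**Cost.** One re-run of an existing model. Event times are already needed for the Kaplan-Meier analysis in SAP item 4, and the 1-month survey identifies women who report early CGRA.

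**Downside.** The sensitivity analysis loses some early events, mostly in TCN, and some power. It conditions on an event after randomisation and applies only to women without CGRA at 1 month.
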